2.6. Objectives

The **primary objective** is to evaluate the tolerability of infigratinib in patients with low-grade and high-grade platinum ineligible UTUC.

The **secondary objectives** are to:

- Assess tolerability in those with GFR 30-49
- Evaluate the objective response rate (CR+PR) of infigratinib after 2 cycles in UTUC with and without FGFR3 alterations
- Correlate tumor tissue FGFR3 alteration (presence/absence, alteration type, and clonal status) with response and occurrence/severity of AEs such as hyperphosphatemia

- Evaluate, bladder and local/distant recurrence within 12 months in those undergoing NUX/Ux and upper tract, bladder, and local/distant recurrence within 12 months in those undergoing endoscopic management.
- Evaluate renal function pre-treatment and after two treatments.
- Evaluate patient-reported quality of life (QOL) outcomes during treatment.

The **exploratory objectives** are to:

- Explore intra-tumor heterogeneity, gene expression profiles, and changes in tumor microenvironment using single cell RNA sequencing (scRNA-seq) and CyTOF pre and post treatment to identify potential mechanisms of response and/or resistance, and correlation with the occurrence/severity of AEs.
- Explore urinary/upper tract washing FGFR3 alterations as potential biomarker for detection and response
- Explore cfDNA for detection of FGFR3 alterations and as a predictor of response

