8. STUDY ASSESSMENTS

8.1. Efficacy Assessments

Efficacy will be assessed by tumor response to study drug. To assess each subject's response, the surgical specimen will be assessed/compared against the pre-treatment tumor mapping (Section 12.3, Appendix 3)

Table 3: Response Criteria for UTUC Lesions

Response criteria	Evaluation of target lesions
Complete Response (CR):	Disappearance of all target lesions as documented in Tumor Mapping.
Partial Response (PR):	At least a 30% decrease in the sum of diameter of all mapped lesions, taking as reference the baseline sum of diameters.
Progressive Disease (PD):	At least a 20% increase in the sum of diameters of mapped lesions, taking as reference the smallest sum on study (this includes the baseline sum if that is the smallest on study). In addition to the relative increase of 20%, the sum must also demonstrate an absolute increase of at least 5 mm. ^a Or the appearance of one or more new lesions.
Stable Disease (SD):	Neither sufficient shrinkage to qualify for PR nor sufficient increase to qualify for PD, taking as reference the smallest sum diameters while on study.

Abbreviations: CR, complete response; PD, progressive disease; PR, partial response; SD, stable disease.

^a The appearance of one or more new lesions is also considered progression.

Source: [Eisenhauer et al 2009](#)

Table 4 (NOT APPLICABLE TO THIS STUDY, KEPT FOR TABLE REFERENCING): Response Criteria for Non-target Lesions

Response criteria	Evaluation of non-target lesions
Complete Response (CR):	Disappearance of all non-target lesions and normalization of tumor marker level.
Progressive Disease (PD):	Unequivocal progression of existing non-target lesions or the appearance of one or more new lesions.
Non-CR/Non-PD:	Persistence of one or more non-target lesion(s) and/or maintenance of tumor marker level above the normal limits.

Abbreviations: CR, complete response; PD, progressive disease.

Source: [Eisenhauer et al 2009](#)

Note: Unequivocal progression in non-target lesions must be substantial and generally sufficient to require change in

therapy. The increase in overall disease burden should be comparable in magnitude to the increase that would be required to declare PD for measurable disease: i.e. an increase in tumor burden representing an additional 73% increase in 'volume' (which is equivalent to a 20% increase diameter in a measurable lesion).

Table 5: Overall Lesion Response at each Assessment

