8.2.7. Ophthalmic Assessments

Ophthalmologic examination will be performed by an ophthalmologist, or optometrist who is supervised by an ophthalmologist, at the times indicated in [Section 1](#). These assessments will include visual acuity testing, slit lamp examination of the anterior eye segment, intraocular pressure, and fundoscopy. Additional examinations such as specular microscopy (that enables a magnified, direct view of the corneal epithelium), corneal pachymetry, retinal optical coherence tomography (OCT), and dilated fundoscopy will be performed as clinically indicated.

9. STATISTICAL PLAN:

The primary objective is to evaluate the safety and tolerability of infigratinib as neoadjuvant therapy. Up to 20 patients will be enrolled in the study. The study will estimate proportion of patients who are not able to complete treatment (discontinuation) due to excessive toxicity along with the 90% exact confidence interval (NOTE: excessive toxicity is defined as treatment related adverse events that cause patients not to complete 2-cycles of planned treatment schedule). Toxicities will be tabulated using frequency and percentage by grade and their relations to treatment. Assuming a 30% of discontinuation due to excessive toxicity, the 90% confidence interval would be (13.1%, 46.9%) with a sample size of 20. Toxicity data will be summarized for the whole group of patients and for patients with eGFR \geq 50 and eGFR 30-49 separately. The safety analysis included all patients who received at least one dose of infigratinib.

Toxicity monitoring:

The study will monitor the incidence of not completing treatment or delay >14 days of surgery due to excessive toxicity using this monitoring rule. That is stop the trial early if $\text{Prob}(\text{Ptox} > 0.3 | \text{data}) > 0.85$. Where Ptox denotes the proportion of patients not being able to complete treatment or delay >14 days of surgery. The corresponding stopping boundaries are that the trial will be stopped early if at any time it is observed that $(n \text{ of patients not completing treatment or delay } >14 \text{ days of surgery due to excessive toxicity} / N \text{ of patients treated}) \geq 3/5, 4/(6-8), 5/(9-10), 6/(11-13), 7/(14-16), \text{ and } 8/(17-19)$. This stopping rule will be applied for each cohort of eGFR \geq 50 and eGFR 30-49 separately. If one cohort stops early due to excessive toxicity, the other will continue accruing as per protocol criteria and toxicity monitoring rule.

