The following table displays the operating characteristics for safety monitoring, assuming prior distribution for Ptox is beta(0.3, 0.7) and for a maximum sample size of 20. Since we do not have information for proportions of eGFR \geq 50 and eGFR 30-49, it would not be feasible to assess OCs for each cohort.

OCs for toxicity monitoring using a maximum sample size of 20

Rate of discontinued treatment due to toxicity/intolerance	Probability of early stop	Avg. N of patients treated
0.1	0.012	19.8
0.2	0.10	18.7
0.3	0.341	16.0
0.4	0.655	12.4
0.5	0.886	9.0

The secondary efficacy endpoint is objective response after 2 cycle treatment of infigratinib. We will estimate the objective response rate along with the 90% confidence interval. Fisher's exact test will be used to explore the difference in response between the two cohorts of patients.

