Descriptive statistics will be used to summarize quantifications as continuous variables and frequency and percentage along with 90% CI will be used to summarize categorical variables. Wilcoxon rank sum test and Fisher's exact test will be used to explore the association between objective response and secondary outcomes, e.g. cfDNA, expression of markers, FGFR3 alteration type. The same methods will also be used to explore the association of AEs such as hyperphosphatemia with response. Recurrence at 12 months will be summarized using proportion and 90% confidence interval as a binary outcome, and also be estimated using the Kaplan-Meier method as a time to event variable. The association between time to event variables and markers will be explored using log rank test and univariable Cox model. With the small sample size, the analysis will probably only descriptive. The analysis will be performed in all patients and by FGFR3 alteration status if applicable. For data collected using the EORTC QLQ-C30 questionnaire, we calculate raw score (RS) and linear transformed score (Score) for each of the five functional scales, three symptom scales, a global health status / QoL scale, and six single items at each time point [Reference: Fayers PM, Aaronson NK, Bjordal K, Groenvold M, Curran D, Bottomley A, on behalf of the EORTC Quality of Life Group. The EORTC QLQ-C30 Scoring Manual (3rd Edition). Published by: European Organisation for Research and Treatment of Cancer, Brussels 2001]. For each of these scales, paired t test or Wilcoxon signed rank test will be used to evaluate the changes of the Scores between two time points. Linear mixed models will also be fitted to evaluate the changes in Scores over time.

9.1.1.1. Adverse Events: Safety analyses will be performed for all subjects who receive at least one dose of study drug according to the treatment they receive.

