12.4 Appendix 4: Correlative and Laboratory Studies

Tumor studies:

- **Tumor mapping** will be performed based on endoscopic findings, noting location, number of tumors, tumor architecture, and location of biopsies; and will again be performed after Infigratinib during pathologic evaluation (NUx/Ux cohort) or URS evaluation (endoscopic cohort, with reasonable attempt to biopsy any residual tumor) again noting size, location, number of tumors, architecture, and absence of tumor at any previously identified tumor. A difference of 3mm will be considered within error of measurement.
- **Mutational analysis** will be performed on FFPE tumor tissue using a comprehensive mutation panel (T200.2) which we have used in prior studies and includes all previously identified UTUC mutations, including all relevant FGFR3 alterations including hot spots, copy number variations and fusions. Blood collected at baseline will be used as germline source
- **Single cell (sc)RNAseq** will be performed on fresh frozen tumors using 10x Genomics platform. Tumor cell heterogeneity, FGFR3 gene expression, and tumor microenvironment will be profiled. All bioinformatics data analysis will be performed in the MD Anderson Rare Tumor Initiative Program.
- **Multiplex IHC** will be performed from FFPE tissue (biopsy and final pathologic specimen or repeat biopsies in the endoscopic cohort) and undergo interrogation for immunologic studies, including lymphocyte subtypes and expression of relevant markers such as PD1, PD-L1, ICOS, among others. These data will be compared between FGFR3 mutant and wild-type tumors to evaluate the differences of the immunological environment between these two groups of tumors.
- **Tissue prioritization:** Given the potentially limited biopsy samples, use of biopsy and pathologic tumor tissue will be prioritized in the following order and sources: 1. Mutational analysis (FFPE), 2. RNAseq (fresh frozen), 3. TMA (FFPE).

Urinary biomarkers:

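### Section 9 tests only CR+PR yes/no against FGFR3 status, cohort and markers; adding a rank analysis of percent change in mapped tumor size would use data already collected

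*Combined protocol and SAP*

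**What the plan says.** Lesion size is recorded at baseline ureteroscopy (Appendix 3a). It is recorded again after treatment, by pathology in the NUx/Ux group or by ureteroscopy in the endoscopic group (Appendices 3b and 4), "again noting size, location, number of tumors, architecture, and absence of tumor at any previously identified tumor".

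Section 8.1, Table 3 turns these sizes into categories. Partial response is "At least a 30% decrease in the sum of diameter of all mapped lesions, taking as reference the baseline sum of diameters". Complete response is "Disappearance of all target lesions as documented in Tumor Mapping". Progression includes a 20% rise in the sum, "Or the appearance of one or more new lesions".

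One secondary objective in Section 2.6 is to "Correlate tumor tissue FGFR3 alteration (presence/absence, alteration type, and clonal status) with response". Section 9 (Statistical Plan) states: "Up to 20 patients will be enrolled in the study". It plans the objective response rate with a 90% confidence interval, and then "Fisher's exact test will be used to explore the difference in response between the two cohorts of patients". For markers, "Wilcoxon rank sum test and Fisher's exact test will be used to explore the association between objective response and secondary outcomes", with cfDNA, marker expression and FGFR3 alteration type as examples. Section 9 specifies no analysis of the percent change itself. It gives no significance level, effect size or power for any of these tests.

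**The concern.** Response here is largely a cut through a graded measure. Patients with 29% and 31% shrinkage count as opposites, and those with 31% and 95% count as the same. For FGFR3 altered versus not, both variables are then binary, which leaves only a 2x2 table with about five patients in one group. The Wilcoxon test named for markers does not recover the loss, because it keeps the marker continuous while response stays yes/no.

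Sections 2 and 2.5.1 say the trial should inform a later phase 2 efficacy study. A gradient in shrinkage by FGFR3 status would be useful for that, and the planned tables are poorly placed to show it.

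**Working it through.** **Inputs from the documents.** Maximum n = 20 (Section 9). FGFR3 alteration prevalence 74.1% (Section 2): 0.741 x 20 = 14.8, so about 15 versus 5. Response rate 25.4%, 17 of 67 (Section 2.4.3); this is the only urothelial rate given, and it comes from advanced or metastatic FGFR3-altered disease. Measurement error 3 mm (Section 2.7).

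**Assumptions.** Two-sided 0.05, all 20 patients evaluable with both maps, and the effect sizes shown. The plan has no power figure on this point to reproduce.

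**Step 1: what Fisher's test needs at 15 versus 5 (no model for shrinkage).** Suppose none of the 5 unaltered patients responds.
- 8/15 versus 0/5: p = [C(15,8) + C(15,3)]/C(20,8) = (6435 + 455)/125970 = 0.055.
- 9/15 versus 0/5: p = [C(15,9) + C(15,4)]/C(20,9) = (5005 + 1365)/167960 = 0.038.

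So at least 9 of 15 must respond. At 25.4%, P(X >= 9) for a binomial with n = 15 is 0.0047, or 0.5%.

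**Step 2: power under graded shrinkage.** Percent change is taken as normal with equal SD and a floor at CR. Response rates p1 and p2 then correspond to a standardized shift d = z(p1) - z(p2); for 25.4% versus 5%, d = -0.66 + 1.64 = 0.98. Fisher power is the exact sum of binomial probabilities over all tables with p <= 0.05. Rank-sum power is simulated.

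| Response, altered vs not (15 vs 5) | d | Fisher on CR+PR | Rank sum on % change |
|---|---|---|---|
| 25.4% vs 10% | 0.62 | 0.4% | 17% |
| 25.4% vs 5% | 0.98 | 0.4% | 38% |
| 40% vs 10% | 1.03 | 6% | 41% |
| 50% vs 20% | 0.84 | 11% | 29% |
| 50% vs 10% | 1.28 | 19% | 58% |
| 60% vs 20% | 1.09 | 24% | 46% |
| 70% vs 20% | 1.37 | 41% | 64% |

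At two-sided 0.10, in line with the plan's 90% intervals, the gap remains: 1.5% versus 54% for 25.4% against 5%, and 30% versus 75% for 50% against 10%.

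**Step 3: how far the gain depends on assumptions.**
- *Measurement noise.* Adding an assumed SD of 30 points to an underlying SD of 35 lowers rank-sum power from 58% to 38% (50% vs 10%) and from 38% to 24% (25.4% vs 5%). Fisher is then about 13% and 0.7%.
- *All-or-none response.* The model is a mixture centred at -65% (SD 20) and 0% (SD 15), floored at -100%. Fisher versus rank sum is 0.4% vs 6% (25.4/5), 16% vs 21% (50/10) and 20% vs 23% (60/20), a gain of about 3 to 6 points.
- *Fisher's conservatism.* With no true difference, its real size at 15 versus 5 is 1.6% to 2.5%, so part of the gap comes from the test and not from the 30% cut.

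**Step 4: continuous markers, n = 20.** Planned Wilcoxon of marker by response versus Spearman of marker with percent change, at a 25% response rate: 21% vs 39% (rho 0.4), 32% vs 57% (rho 0.5), 46% vs 76% (rho 0.6). Over rho 0.4 to 0.7 and response rates of 25% to 50%, the relative loss is 18% to 46%.

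**The case against.** The primary objective is tolerability. Section 9 describes the response tests as exploratory and expects the analysis at this sample size to be mainly descriptive. It claims no power, so none of its figures is wrong. This stands and sets the weight of the point. It does not remove it: the tests are still named, and a descriptive report also gains from showing percent change.

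The RECIST-type categories are conventional. That justifies the response rate as the reported endpoint, but it does not require every association test to use the cut.

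Measurement is the most serious objection. Baseline size is endoscopic, while follow-up size is pathologic in one group and ureteroscopic in the other. The 3 mm allowance is 30% of a 10 mm lesion. The same error already enters the 30% cut, and the rank test keeps an advantage under noise, but a smaller one. Route could also be unbalanced by FGFR3 status, because alterations are commoner in low-grade tumors (92% versus 60%, Section 2), for which endoscopic management is described. With an assumed altered/unaltered split of 9/1 in one route and 6/4 in the other, stratifying by route lowers power in the 50% vs 10% case from 58% to 50%.

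For the cohort comparison the objection can be decisive. The two cohorts are not defined where the test is named: Section 9 uses the word for the eGFR strata, Section 2.7 and Appendix 4 for NUx/Ux versus endoscopic. In the second sense cohort and measurement route coincide. Stratifying then leaves nothing to compare. An unstratified rank test, with an assumed route shift of 15 to 25 points and no true difference, gives 13% to 28% false positives at 10 versus 10, against 3% to 10% for Fisher.

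A reader might infer that all the association analyses lose most of their power, or that a real gradient would be reported as no association. The documents support neither. The loss is below half for continuous markers and for Fisher comparisons at high response rates (41% versus 64% at 70% vs 20%), and nothing in the plan says that a non-significant result will be read as absence of association.

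**Conclusion.** The point holds as a cheap improvement to an exploratory analysis, not as an error. For FGFR3 status at about 15 versus 5, if shrinkage is graded and the higher response rate is about 25% to 50% (against 5% to 10%), Fisher's test on CR+PR has roughly 0% to 19% power. A rank test on percent change has about 38% to 58% for the clearer differences in that range, and 17% for 25.4% vs 10%. At 60% vs 20% the figures are 24% and 46%. These rest on an assumed level of two-sided 0.05, a normal shift, and complete pairs of maps. The documents do not show which shape of response is true, and under all-or-none response the gain nearly vanishes. Power stays below 60% in most of the scenarios even after the change, so the FGFR3 question remains largely descriptive.

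**What to change.** Keep the objective response rate with its 90% interval and the planned tests on CR+PR. Before outcome data are examined, add to Section 9 an exploratory analysis of each patient's percent change from baseline in the sum of mapped diameters:

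- Set CR to -100% and rank any patient with new lesions worst.
- Use the Wilcoxon rank sum test for FGFR3 altered versus not, and Spearman correlation for continuous markers.
- Show results also by measurement route (pathology or ureteroscopy), with a waterfall plot by FGFR3 status.
- Define the two cohorts. If they are the eGFR strata, apply the rank test there too. If they are NUx/Ux versus endoscopic, do not test percent change between them.

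The cost is a paragraph of wording and a few outputs from forms already completed, with no new patients or procedures. The downside is that pathology and ureteroscopy sizes may differ systematically, so the analysis should stay supportive.

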9.1.1.2. Other Safety Findings

Laboratory parameters for hematology and serum blood chemistry will be summarized at baseline, by visit, and at the last observed value. Additionally, the maximum and minimum observed post baseline values will be summarized along with the change from baseline to the maximum observed value, minimum observed value and last observed value. Tables of shifts in severity (by CTCAE version 5.0) from baseline for selected laboratory parameters and selected

time points may also be provided. Graphical representations of aggregate data may also be presented for parameters of interest.

Vital signs, physical examination results, ophthalmic assessment and ECG and cardiac imaging results will be summarized by treatment group using descriptive statistics (including changes from baseline).

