2. BACKGROUND

Upper tract urothelial carcinoma (UTUC) is typically considered similar as bladder urothelial cancer just occurring upstream in the ureter or renal pelvis, but there are unique molecular and clinical aspects that differentiate it from its more common counterpart. Unique aspects of UTUC include causation by exposure to aristolochic acid (found in many eastern herbal remedies and accounting for the high rates in the East), high rates of microsatellite instability, strong predisposition in those with Lynch syndrome, and high rates of FGFR3 mutations.

Generally, treatments are allocated based on biopsy showing low grade versus high grade disease. Treatments for those with low-grade disease include endoscopic management only, which allows preservation of kidney function but is associated with multiple procedures and high rates of recurrence. Endoscopic treatment of UTUC is often imperatively needed to avoid placing older patients on dialysis, or in those with low-grade, low-volume disease who wish to retain their kidney and avoid major surgery. Limitations of endoscopic management include the need to perform multiple procedures in staged fashion, an inability to manage large volume disease, and a 30-80% recurrence rate. No standard adjuvant therapy exists in this population although many, including us, have tried topical therapies with variable success rates of 40-70% RFS. The standard accepted treatment however is surgery with nephroureterectomy or ureterectomy (NUx/Ux), which creates or worsens existing renal insufficiency in many cases, and is associated with high complication rates given the typically elderly population. Ureteroscopic (URS) management is an option that can preserve the kidney but is associated with significant recurrence rates.

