5. TREATMENTS

5.1. Treatments Administered

Patients will receive infigratinib 125 mg orally every day for a total of 2 cycles. Each cycle will consist in 28 days, with a schedule of 3 weeks on, 1 week off. Surgery will be performed during weeks 8-9 (week 8 being the off-week of 2nd cycle), and patients will have taken last dose of Infigratinib at least 48 hours prior to surgery.

If patients are not able to tolerate the study drug, every effort will be made to schedule the surgery as soon as possible after the patient has recovered and/or the investigator determines it is the best course of action for the patient.

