7.7. End of Study

All subjects must complete one last visit approximately one year (+/- 30 days) after discontinuation or study treatment or surgery, whichever occurred last. Assessments will include the following:

- Relevant medical history/current medical conditions
- Physical examination
- Vital signs
- Blood draw for hematology, chemistry
- CT scan and cystoscopy(+/- URS)

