AEs will be considered to be treatment emergent if the event occurs on or after the first administration of protocol specified treatment and within last dose date + 30 days. The subject incidence rates of AEs will be tabulated by system organ class, preferred term and severity grade for all treatment emergent, serious, treatment related, and serious treatment related AEs. Each of these outputs will include tabulation by maximum severity for each system organ class and preferred term as reported by the investigator based on CTCAE, version 5.0. Summary tables will be provided separately for AEs leading to study drug discontinuation. All "on study drug" deaths, ie, deaths that occur within 30 days after last dose of study drug, will be summarized. Listings and/or narratives of "on study drug" deaths, serious and significant AEs, including study drug discontinuation due to AEs, will also be provided.

The summaries of the subject incidence rates of treatment emergent AEs by system organ class and preferred term reported AEs will also be provided for subgroups defined by age, sex, and race (if feasible).

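### The maximum, minimum and last-value laboratory summaries have no end of window, so they mix on-treatment draws with draws taken about 30 days and 1 year after surgery

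*Combined protocol and SAP*

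**What the plan says.** Section 9.1.1.2 (Other Safety Findings) begins: "Laboratory parameters for hematology and serum blood chemistry will be summarized at baseline, by visit, and at the last observed value". It adds that "the maximum and minimum observed post baseline values will be summarized along with the change from baseline to the maximum observed value", and likewise the changes to the minimum and last values. Neither sentence mentions surgery, last dose or any other end point. Shift tables are optional and use selected time points.

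The schedule in Section 1 marks safety laboratories after baseline at Day 29, at the pre-op visit (Day 57), 30 days post-op and 365 days post-op. Section 7.6 lists hematology and chemistry at the 30-day visit, and Section 7.7 does so for the 1-year visit ("Blood draw for hematology, chemistry"). Table 6 includes creatinine in the chemistry panel.

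Section 9 does set a window elsewhere. Section 9.1.1.1 states that "AEs will be considered to be treatment emergent if the event occurs on or after the first administration of protocol specified treatment" and no later than 30 days after the last dose. Deaths on study drug have the same 30-day limit. No such limit is given for laboratory values.

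On the operation, Section 5.1 says "Surgery will be performed during weeks 8-9 (week 8 being the off-week of 2nd cycle". The Background says that nephroureterectomy or ureterectomy (NUx/Ux) "creates or worsens existing renal insufficiency in many cases". The renal objective in Section 2.6 is "Evaluate renal function pre-treatment and after two treatments".

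**The concern.** A maximum, minimum or last post-baseline value in a safety section is normally read as what happened on the drug. Here an operation with a known renal effect falls between the second and third scheduled full panels, and nothing stops the later panels from entering the pooled rows. The study has one arm, so no comparator can separate surgery from drug.

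The rest of the plan does separate them. Section 8.2.1.3 leaves out AEs due only to surgery, Section 8.2.1.4 does the same for SAEs, and the schedule marks no AE assessment at 1 year. The laboratory rows are the exception.

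Creatinine elevation (42%) and anemia (36%) are among the events quoted in the Background from the earlier urothelial study of this drug, so creatinine and hemoglobin will be looked at closely. Section 9 also summarizes toxicity separately for eGFR 30-49, where a misread renal row would mislead most. Section 8.2.1.3 captures AEs only from Grade 3 and only if drug-related, so milder laboratory changes will be seen largely through these summaries.

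**Working it through.** The plan gives no figure to reproduce. The check is a count of draws, day arithmetic, and an illustration on stated assumptions.

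**1. Draws.** The scheduled full panels after baseline are Day 29, pre-op, 30 days post-op and 365 days post-op. The Day 14 draw is phosphate only. Two of four follow surgery (50%).

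**2. Last dose.** Section 5.1: "Each cycle will consist in 28 days, with a schedule of 3 weeks on, 1 week off". Cycle 2 starts on Day 29 and has 21 dosing days, so the nominal last dose is Day 28 + 21 = Day 49.

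**3. Surgery.** Weeks 8-9, at least 48 hours after the last dose, gives about Days 51 to 63.

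**4. Timing of the last value.** With surgery on Day 57, the 1-year draw is on Day 57 + 365 = 422, and 422 - 49 = 373 days after the last dose. With the ± 30-day window and surgery on Days 51 to 63, the draw falls between Day 386 (51 + 335) and Day 458 (63 + 395), which is 337 to 409 days after the last dose.

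**5. Would the AE window be enough?** Last dose + 30 is Day 79, which is 28 days after surgery on Day 51 and 16 days after surgery on Day 63. The earliest post-op draw is Day 51 + 30 - 14 = Day 67, inside that window. Borrowing the AE window would therefore not keep post-surgical draws out.

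**6. Creatinine after loss of a kidney (assumption).** If creatinine varies inversely with GFR, the ratio is 1/(1 - loss). Assumed losses of 20%, 30% and 40% give 1.25, 1.43 and 1.67, a rise of 25%, 43% and 67% with no drug effect.

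**7. Illustration for one NUx patient (assumptions).** 200,000 simulated patients, no drug effect, log-normal within-patient variation of 8% or 15%, four scheduled post-baseline panels, and the two post-surgery values multiplied by 1 + r. Ranges run over the two levels of variation.

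| Assumed rise r | Maximum is a post-surgery draw | Median change to maximum, all draws | Same, cut before surgery | Median change to last value, all draws | Same, cut before surgery |
|---|---|---|---|---|---|
| 0% | 50% | 8.5-16.4% | 4.6-8.6% | 0% | 0% |
| 10% | 71-85% | 15.7-23.4% | 4.5-8.6% | 10% | 0% |
| 25% | 90-99% | 30.7-36.9% | 4.6-8.6% | 25% | 0% |
| 40% | 97-100% | 46.3-52.4% | 4.5-8.7% | 40% | 0% |

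The 0% row shows the effect of pooling four noisy draws instead of two.

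**8. Whole group.** If a share s of patients has NUx with rise r and the others have none, the mean change to the last value is s × r. At r = 25% this runs from 0 (s = 0) to 25% (s = 1).

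**The case against.** The strongest reply is that the same section plans by-visit summaries. Pre-op and post-op values will stand in separate rows, and a step after surgery will be visible there. That is correct, and it confines the problem to the pooled maximum, minimum and last-value rows and any shift table built on them.

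A reader might infer that the plan reports the effect of kidney removal as a drug effect. Section 9.1.1.2 does not say so. It only summarizes the values, and causality is assigned through the AE process.

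A reader might also infer that the primary result or the renal objective is compromised. The primary endpoint is failure to complete treatment because of treatment-related events, and the stopping rule adds surgical delay; neither uses these rows. The renal objective names its own two time points, and the by-visit pre-op panel can supply the second.

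A third inference would be that the post-operative creatinine will usually be the maximum, or that the lowest hemoglobin will mostly reflect the operation. The documents do not support either as a general statement. They give no NUx share, and patients may instead have ureterectomy or ureteroscopic management, which do not remove the kidney. They give no figure for GFR or hemoglobin loss. The draw count also leaves out extra on-treatment samples: unscheduled draws (Section 8.2.3) and repeat creatinine after Grade 2 or higher with hyperphosphatemia (Table 2). These add pre-surgery values in the patients most likely to show a drug effect.

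Finally, a cut at surgery could move a late drug effect out of the on-treatment table. This is a real cost, because the post-op draw can fall within 30 days of the last dose.

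What remains is that the rule as written has no end of window, and the post-surgical draws qualify for it.

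**Conclusion.** The point holds for the pooled laboratory rows. Two parts need no assumption beyond the schedule: half of the scheduled post-baseline full panels follow surgery, and every completer's last value is the 1-year draw, nominally 337 to 409 days after the last dose. This is so whichever procedure the patient had.

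The effect on maximum creatinine is conditional. In an NUx patient with an assumed 25% rise and no drug effect, the median change to maximum would be about 31-37%, against about 5-9% if cut before surgery. At a 10% rise the contrast is about 16-23% against 5-9%. The size in the full group cannot be stated without the NUx share.

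This is a fault in descriptive safety reporting for up to 20 patients and does not threaten the trial's main conclusion. It is worth correcting because the rows as specified would be hard to interpret in a single-arm study.

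**What to change.** Amend Section 9.1.1.2 as follows.

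- Limit the maximum, minimum and last-value summaries, the changes from baseline to them, and any shift table based on them, to scheduled and unscheduled draws after first dose and before surgery. For patients without surgery, end the window at last dose + 30 days.
- State that the renal value after two cycles is the pre-op creatinine/eGFR.
- Keep the 30-day and 1-year post-op values in the by-visit output or in a separate table, split by NUx, ureterectomy and endoscopic management.

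The cost is wording and some programming; no new data are needed. Two of the four scheduled full panels will no longer feed the extremes. A post-op draw within last dose + 30 days moves to the post-surgery table, where it is still reported; flagging such draws there would keep a late drug effect in view.
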